6.5 POOLING OF CENTRES

This section is not applicable, because the study was performed in only one centre.

6.6 HANDLING OF MISSING DATA AND OUTLIERS

Data of screened subjects who were withdrawn from the trial prior to first administration of any study drug will not be reported in the CTR.

Data of subjects who failed to complete the study (dropouts or withdrawals) will be reported in the CTR as far as their data are available. All withdrawals will be documented and the reason for withdrawal recorded in the CTR.

CTP: With respect to safety evaluations, it is not planned to impute missing values.

The only exception where imputation might be necessary for safety evaluation are AE dates. Missing or incomplete AE dates are imputed according to BI standards (4) [001-MCG-156_RD-01].

Missing data and outliers of PK data are handled according to BI standards (5).

Blood/ Plasma/ Urine/ Faeces drug concentration-time profiles

CTP: *Drug concentration data identified with NOS (no sample available), NOR (no valid result), NOA (not analysed), BLQ (below the lower limit of quantification), or NOP (no peak detectable) will be displayed as such and not replaced by zero at any time point (this rule also applies also to the lag phase, including the predose values).*

Pharmacokinetic parameters

CTP: *For the non-compartmental analysis, concentration data identified with NOS, NOR or NOA will generally not be considered. Concentration values in the lag phase identified as BLQ or NOP will be set to zero. All other BLQ/NOP values of the profile will be ignored. The lag phase is defined as the period between time zero and the first time point with a concentration above the quantification limit.*

6.7 BASELINE, TIME WINDOWS AND CALCULATED VISITS

The last non-missing value determined prior to the first study drug administration will be defined as baseline.

Time windows are defined in Section 6.1 of the CTP. Adherence to time windows will be checked at the RPM/DBLM.

7. PLANNED ANALYSIS

The format of the listings and tables will follow the BI guideline "Reporting of clinical trials and project summaries" ([6](#)).

The individual values of all subjects will be listed, sorted by dose group, subject number and visit. AE listings will be sorted by assigned treatment (see [Section 7.8.1](#) below for details). The listings will be contained in Appendix 16.2 (SDL) of the CTR.

The following standard descriptive statistical parameters will be displayed in summary tables of continuous variables:

N	number of non-missing observations
Mean	arithmetic mean
SD	standard deviation
Min	minimum
Median	median
Max	maximum

For plasma concentrations as well as for all PK parameters, the following descriptive statistics will additionally be calculated:

CV	arithmetic coefficient of variation
gMean	geometric mean
gCV	geometric coefficient of variation

The data format for descriptive statistics of plasma concentrations will be identical with the data format of the respective concentrations. The descriptive statistics of PK parameters will be calculated using the individual values with the number of decimal places as provided by the evaluation program. Then the individual values as well as the descriptive statistics will be reported with three significant digits in the CTR.

Tabulations of frequencies for categorical data will include all possible categories and will display the number of observations in a category as well as the percentage (%) relative to the respective treatment. Percentages will be rounded to one decimal place. The category missing will be displayed if and only if there actually are missing values. Percentages will be based on all subjects in the respective subject set whether they have non-missing values or not.

7.1 DEMOGRAPHIC AND OTHER BASELINE CHARACTERISTICS

Only descriptive statistics are planned for this section of the report. These will be based on the TS.

7.2 CONCOMITANT DISEASES AND MEDICATION

Concomitant diseases will be coded according to MedDRA version 21.1. Concomitant medication will be coded according to World Health Organisation – Drug Dictionary, version of March 2018.

Only descriptive statistics are planned for this section of the report.

A medication will be considered concomitant to a dose group, if it

- is ongoing at the time of first administration of this treatment, or
- starts within the analysis phase of the respective treatment (see [Section 6.1](#) for a definition of treatments and analysis phases).

7.3 TREATMENT COMPLIANCE

Treatment compliance will not be analysed as a specific endpoint (cf. [Section 5.4.2](#)). Any deviations from complete intake will be addressed in the RPM/DBLM (cf. [Section 6.2](#)) and described in the CTR.

7.4 PRIMARY ENDPOINTS

Primary endpoints will be evaluated descriptively only. These will be based on the PKS. The analysis of standard PK parameters is performed according to BI standards ([5](#)) [001-MCS-36-472_RD-01].

Exclusion of PK parameters

The ADS ADPP contains column variables APEXC and APEXCO indicating inclusion/exclusion (APEXC) of a PK parameter and an analysis flag comment (APEXCO). All analyses based on the PKS are based on PK parameter values which are not flagged for exclusion, i.e. with APEXC equal to "Included".

Exclusion of plasma concentrations

The ADS ADPC (PK concentrations per time-point or per time-interval) contains column variables ACEXC or ACEXCO indicating inclusion/exclusion (ACEXC) of a concentration and an analysis flag comment (ACEXCO). Exclusion of a concentration depends on the analysis flag comment ACEXCO. For example, if ACEXCO is set to "ALL CALC", the value will be excluded for all types of analyses based on concentrations. If ACEXCO is set to "DESC STATS" the value will be excluded from descriptive evaluations per planned time point/time interval. If ACEXCO contains the addition "TIME VIOLATION" or "TIME DEVIATION", the value can be used for further analyses based on actual times. If ACEXCO is set to "HALF LIFE", the value will be excluded from half-life calculation only; the value is included for all other analyses. Excluded concentration itself will be listed in the CTR associated with an appropriate flag.

Further details are given in "Noncompartmental Pharmacokinetic / Pharmacodynamic Analyses of Clinical Studies" ([5](#)) and "Description of Analytical Transfer Files and PK/PD Data Files" ([7](#)).

7.5 SECONDARY ENDPOINT(S)

7.5.1 Key secondary endpoint

This section is not applicable as no key secondary endpoint has been specified in the CTP.

7.5.2 Secondary endpoints

Secondary PK endpoints will be assessed descriptively. This will be based on the PKS. The analysis of standard PK parameters is performed according to BI standards ([5](#)) [001-MCS-36-472_RD-01].

See [Section 7.4](#) of this TSAP for details regarding exclusion of PK parameters and plasma concentrations.

7.6 FURTHER ENDPOINT(S)

7.6.1 Safety endpoints

Safety endpoints will be analysed as described in Section 7.8 of this TSAP.

7.7 EXTENT OF EXPOSURE

Treatment exposure will only be listed by means of the date and time of drug administration.

7.8 SAFETY ANALYSIS

All safety analyses will be performed on the TS.

7.8.1 Adverse events

AEs will be coded with MedDRA version 21.1.

The analyses of AEs will be descriptive in nature. All analyses of AEs will be based on the number of subjects with AEs and not on the number of AEs.

For analysis, multiple AE occurrence data on the electronic case report form (eCRF) will be collapsed into an AE event provided that all of the following applies:

- All AE attributes are identical (LLT, intensity, action taken, therapy required, seriousness, reason for seriousness, relationship, outcome, AESI)
- The occurrences were time-overlapping or time-adjacent (time-adjacency of two occurrences is given if the second occurrence started at most 1 hour after the first occurrence ended).

For further details on summarization of AE data, please refer to "Analysis and presentation of adverse event data from Clinical Trials" (8) and "Handling of missing and incomplete AE dates" (4).

The analysis of AEs will be based on the concept of treatment emergent AEs. That means that all AEs will be assigned to the screening or treatment phases as defined in [Section 6.1](#). AEs will be analysed based on actual treatments, as defined in [Table 6.1: 1](#).

An overall summary of AEs will be presented. This overall summary will comprise summary statistics for the class of other significant AEs according to ICH E3 (9) and for the class of AESIs.

CTP: *The following are considered as AESIs:*

- *Hepatic injury*
A hepatic injury is defined by the following alterations of hepatic laboratory parameters:
 - *an elevation of AST (aspartate transaminase) and/or ALT (alanine transaminase) ≥ 3 -fold ULN combined with an elevation of total bilirubin ≥ 2 -fold ULN measured in the same blood sample, or*
 - *aminotransferase (ALT, and/or AST) elevations ≥ 10 fold ULN*

The investigator had to classify on the eCRF whether an observed AE was an AESI or not.

According to ICH E3 (9), AEs classified as 'other significant' need to be reported and will include those non-serious and non-significant AEs

- (i) which are marked haematological or other lab abnormalities, or
- (ii) which were reported with 'action taken = discontinuation' or 'action taken = reduced', or
- (iii) which lead to significant concomitant therapy as identified by the Clinical Monitor/Investigator at a Medical Quality Review Meeting.

The frequency of subjects with AEs will be summarised by treatment, primary system organ class and preferred term. AEs which were considered by the investigator to be drug related will be summarised separately. Separate tables will also be provided for subjects with SAEs, subjects with AESIs and subjects with other significant AEs (according to ICH E3 (9)). AEs will also be summarized by maximum intensity.

The system organ classes will be sorted by total frequency, preferred terms will be sorted by total frequency (within system organ class).

For disclosure of AE data on ClinicalTrials.gov, the frequency of subjects with non-serious AEs occurring with an incidence of greater than 5 % (in preferred terms) will be summarised by treatment, primary SOC and preferred term. The frequency of subjects with SAEs will also be summarised.

For disclosure of AE data in the EudraCT register, the frequency of AEs, the frequency of non-serious AEs with an incidence of greater than 5 % (in preferred terms) and the frequency of SAEs will be summarised.

7.8.2 Laboratory data

The analyses of laboratory data will be descriptive in nature and will be based on BI standard "Display and Analysis of Laboratory Data" ([10](#)).

Analyses will be based on normalised values, which means transforming to a standard unit and a standard reference range.

Descriptive statistics of laboratory values over time and for the difference from baseline (see [Section 6.7](#)) will be provided. Frequency tables of changes between baseline and last value on treatment with respect to the reference range will be presented.

Unscheduled measurements of laboratory data will be assumed to be repeat measurements of the most recent scheduled measurement (e.g. for follow-up or confirmation of a particular value). Therefore, unscheduled measurements will be assigned to the planned time point of the previous scheduled measurement. Descriptive statistics will be calculated by planned time point based on the worst value of the subject at that planned time point (or assigned to that planned time point).

Possibly clinically significant abnormal laboratory values are only those identified either in the Investigator's comments on the eCRF or at the RPM/DBLM at the latest. It is the Investigator's responsibility to decide whether a lab value is clinically significant abnormal or not. Standard or project-specific rules for flagging clinically significant values will not be applied in this study.

Clinically relevant findings in laboratory data will be reported as AEs and will be analysed as part of AE analysis.

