Name of finished product: Not applicable			
Name of active ingredient: BI 425809			
Protocol date: 29 June 2018	Trial number: 1346-0016		Revision date: 25Sep2018
Criteria for pharmacokinetics:	
Primary endpoints: Mass balance recoveries of total radioactivity in urine and faeces: Amount of radioactivity excreted as a percentage of the administered dose (fe_{0-t2}) for urine and faeces
 
Secondary endpoints: Assessment of the oral pharmacokinetics of a solution formulation of BI 425809 XX (C-14) by calculation of the following parameters for total radioactivity and BI 425809 in plasma: C_{max} and AUC_{0-tz}
		
Criteria for safety:	Adverse events (AEs) including clinically relevant findings from the physical examination, safety laboratory tests, 12-lead electrocardiogram (ECG), vital signs (blood pressure [BP], pulse rate [PR])		
Statistical methods:	Descriptive statistics and graphical displays.		

FLOW CHART

Visit	Day	Planned time (relative to 1st drug administration [h:min])	Approximate clock time of actual day [h:min]	Event and comment	Safety laboratory	PK _{blood/plasma} ²	PK _{urine} ⁶	PK _{faeces} ⁷	12-lead ECG	Vital signs (BP, PR)	Questioning for AEs and concomitant therapy ⁹
1	-21 to -2			Screening (SCR) ¹	x				x	x	
2	-1	-18:00	14:00	Admission to trial site	x ⁵						x
		-14:00	18:00	Dinner							
		-10:30	21:30	Snack (voluntary) ¹⁵							
	1	-2:00	06:00		x ³	x ³	x ³	x ¹⁴	x ³	x ³	x ³
		0:00	08:00	Drug administration			+	+			
		0:30	08:30			x					
		0:45	08:45			x					
		1:00	09:00			x					
		1:30	09:30			x					
		2:00	10:00	240 mL fluid intake		x					
		4:00	12:00	240 mL fluid intake, thereafter lunch ⁴	x ⁸	x	+		x	x	x
		6:00	14:00			x					
		8:00	16:00	Snack (voluntary) ⁴		x	+				
		11:00	19:00	Dinner							
		12:00	20:00			x	+		x	x	x
		13:30	21:30	Snack (voluntary)							
	2	24:00	08:00			x	+	+		x	x
		36:00	20:00			x					
	3	48:00	08:00		x ⁸	x	+	+			x
	4	72:00	08:00			x	+	+			x
	5	96:00	08:00			x	+	+			x
	6	120:00	08:00			x	+	+			x
	7	144:00	08:00			x	+	+			x
	8	168:00	08:00		x ⁸	x	+	+			x
	9	192:00	08:00			x	+	+			x
	10	216:00	08:00			x	+	+			x
	11	240:00	08:00			x	+	+			x
	12	264:00	08:00			x	+	+			x
	13	288:00	08:00			x	+	+			x
	14	312:00	08:00			x	+	+			x
	15	336:00	08:00	Discharge from trial centre	x	x	+	+	x	x	x
	20	461:00	13:00	Start home collection				+			
	21	485:00	13:00	Admission to trial site ^{11,12}		x	+	+			x
	22	509:00	13:00	Discharge from trial site ¹¹			+	+			x

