- Urine collection intervals (for PK/[¹⁴C]-radioactivity assessment and metabolic profiling; planned time): on Day -1 or Day 1 predose (blank) sample within 2 h before drug administration, on Day 1 prior to start of urine collection voiding of the bladder, 0-4, 4-8, 8-12, 12-24; 24-48, 48-72, 72-96, 96-120, 120-144, 144-168, 168-192, 192-216, 216-240, 240-264, 264-288, 288-312 and 312-336 hours after drug administration. Thereafter, if warranted, 24 h collections are to be performed every 7 days starting on day 21. When the release criteria for radioactivity recovery have been met then urine sampling for PK will be stopped (earliest stop on day 15).
- All stools (for PK and metabolic profiling) will be collected quantitatively in portions up to 336 hours (sampling intervals of 0-24, 24-48, 48-72, 72-96, 96-120, 120-144, 144-168, 168-192, 192-216, 216-240, 240-264, 264-288, 288-312 and 312-336 hours) after drug administration. Thereafter, if warranted, 24 h collections are to be performed every 7 days starting on day 20. A blank sample will be collected before drug administration on Day -1 or Day 1. Collection of the predose faeces sample will start from approximately -48 h before admission (see [Section 5.5.2.3](#)). When the release criteria for radioactivity recovery have been met then faeces sampling for PK will be stopped (earliest stop on day 15).
- Only measurement of haematocrit
- AEs and concomitant therapies will be recorded throughout the trial, but will be specifically asked for at the time points indicated in the [Flow Chart](#) above.
- End-of-trial (EOT) examination to be performed within 1 to 7 days after last discharge from the study centre, or, if all once-weekly 24 h sampling periods are needed, prior to discharge on Day 50. End of trial examination includes physical examination, vital signs, ECG, safety laboratory, recording of AEs and concomitant therapies.
- The planned times for admission, discharge, start and end of the urine and faeces collection intervals are approximate. The procedures are to be performed within a time window of +/- 4 h to the planned time.

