1.2.3 Residual Effect Period

The Residual Effect Period (REP) of BI 425809 is 11 days. This is the period after the last dose with measurable drug levels and/or pharmacodynamic effects still likely to be present.

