2.3 BENEFIT - RISK ASSESSMENT

Participation in this study is without any (therapeutic) benefit for healthy subjects. Their participation in the study, however, is of major importance to the development of BI 425809. The subjects are exposed to the risks of the study procedures and the risks related to the exposure to the trial medication and the intake of BI 425809 XX (C-14).

Procedure-related risks

The total volume of blood withdrawn during the entire study per subject will not exceed the volume of a normal blood donation (500 mL). No health-related risk to healthy subjects is expected from this blood withdrawal.

The use of an indwelling venous catheter for the purpose of blood sampling may be accompanied by mild bruising and also, in rare cases, by transient inflammation of the wall of the vein. In addition, in rare cases a nerve might be injured while inserting the venous catheter, potentially resulting in paraesthesia, reduced sensibility, and/or pain for an indefinite period. The same risks apply to venepuncture for blood sampling.

Drug-related risks and safety measures

Although rare, a potential for drug-induced liver injury (DILI) is under constant surveillance by sponsors and regulators. Therefore, this trial requires timely detection, evaluation, and follow-up of laboratory alterations in selected liver laboratory parameters to ensure subjects' safety, see also [Section 5.2.2.1](#), adverse events of special interest.

Risks related to BI 425809 administration

The currently available data from 7 phase I trials in healthy young and elderly subjects with single oral administration of up to 150 mg BI 425809 and multiple doses of up to 75 mg BI 425809 twice daily (150 mg/d) indicate that BI 425809 has a broad safety margin and is generally well tolerated. The most frequent AEs were adverse CNS symptoms, most commonly headaches but also somnolence (drowsiness) that showed a trend for dose dependency, were reversible and can be clinically monitored. In addition, BI 425809 may be

associated with visual disturbances. These effects are understood to be mostly mild to moderate and transient. Decreased haemoglobin is a potential risk based on preclinical data and class effect; however, no clear decrease in haemoglobin was seen in BI 425809 treated subjects compared to placebo in phase I trials so far.

Risks related to M232 (BI 761036) and M530 (BI 758790)

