6. GENERAL ANALYSIS DEFINITIONS

6.1 TREATMENT

For basic study information on treatments to be administered, assignments of dose groups, and selection of doses, cf. Section 4 of the CTP.

All subjects were planned to be treated with a single dose of [¹⁴C] BI 425809 (25 mg BI 425809 calculated as free base)

For statistical analysis of AEs, safety laboratory data and vital signs, the following analysis phases are defined for each subject:

Table 6.1: 1 Flow chart of analysis phases for statistical analyses of AEs, safety laboratory data and vital signs

Study analysis phase	Label	Start (inclusive)	End (exclusive)
Screening	Screening	Date of informed consent	Date/time of administration of study drug
On-treatment	BI 425809	Date/time of administration of study drug	Date/time of last administration of study drug + 11 * 24 h (i.e., REP of 11 days) or 0:00 AM on day after subject's trial termination date
Follow-up	F/U	Date/time of last administration of study drug + 11 * 24 h	Whatever comes first 0:00 AM on day after subject's trial completion date

CTR Section 15, Appendix 16.1.13.1.8.2 and Appendix 16.1.13.1.8.3 AE displays will present results for the on-treatment phase only. Appendix 16.1.13.1.8.1 will present results for the screening, on-treatment and follow-up phase.

Additionally, the following total will be provided in CTR Section 16.1.13.1.8.1 AE tables:

- **"Total"**, defined as the total over all study phases (incl. screening, on-treatment, and follow-up)

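### The laboratory shift tables use the last on-treatment value, but that phase closes at 264 h, before any scheduled post-dose test other than haematocrit

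*SAP*

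**What the plan says.** SAP 6.1 introduces its phases with "For statistical analysis of AEs, safety laboratory data and vital signs, the following analysis phases are defined for each subject". In Table 6.1: 1 the on-treatment phase starts at drug administration and ends, exclusive, at "Date/time of last administration of study drug + 11 * 24 h (i.e., REP of 11 days"), or at midnight after the subject's trial termination date if that is sooner. Everything later is follow-up. The 11 days come from Protocol 1.2.3: "The Residual Effect Period (REP) of BI 425809 is 11 days".

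Two outputs depend on this phase:

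- SAP 7.8.2, on laboratory data: "Frequency tables of changes between baseline and last value on treatment with respect to the reference range will be presented".
- SAP 6.1, on CTR Section 15 and two of the appendix displays: "AE displays will present results for the on-treatment phase only". A third appendix, 16.1.13.1.8.1, covers all phases and adds a total.

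In the Protocol Flow Chart, the safety laboratory marks at 4, 48 and 168 h carry footnote 8, which reads "Only measurement of haematocrit". The marks at 336 h (Day 15) and 821 h (Day 35) and at the end-of-trial (EOT) examination do not carry it.

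**The concern.** A shift table needs a baseline category and a later category for each subject. If the later value must come from a phase in which the analyte is never scheduled, the table cannot be filled. The analytes affected include those the protocol singles out: liver parameters, which define the only AESI (Protocol 5.2.2.1), and haemoglobin, where Protocol 2.3 names a decrease as a potential risk.

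The same boundary affects the AE displays. SAP 7.8.2 sends clinically relevant laboratory findings into the AE analysis, and hepatic injury is defined by laboratory values. If such an event is found at the first scheduled liver test and dated there, it falls in follow-up, and the Section 15 AESI table could show none although one occurred. In a six-subject study one subject is 1/6, about 17% of the sample.

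**Working it through.** **Inputs**
- Length of the on-treatment phase: 11 × 24 h after the dose (SAP Table 6.1: 1), matching the 11-day REP in Protocol 1.2.3.
- Laboratory schedule: Protocol Flow Chart and footnote 8.
- Window for laboratory tests after Day 1: ±90 min (Protocol 6.1).
- Assignment rule: measurements by planned time, AEs by recorded onset (Protocol 7.3.3).

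**Step 1: the plan's own figure.** 11 × 24 = 264 h. SAP and protocol agree.

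**Step 2: place each scheduled test in a phase.**

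| Planned time | Laboratory content | Phase |
|---|---|---|
| −18 h, −2 h | Safety laboratory | Screening |
| 4 h | Haematocrit only | On-treatment |
| 48 h | Haematocrit only | On-treatment |
| 168 h | Haematocrit only | On-treatment |
| 336 h (Day 15) | Broader panel | Follow-up |
| 821 h (Day 35, only if weekly collections continue) | Broader panel | Follow-up |
| EOT | Broader panel | Follow-up |

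The 336 h panel is not complete either: Protocol Table 5.2.3: 1 restricts hormones, uric acid, cholesterol, triglycerides and urinalysis to screening and end of trial. These also have no on-treatment value.

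**Step 3: the gap.** 336 − 264 = 72 h. At the early edge of the window, 336 − 1.5 = 334.5 h and 334.5 − 264 = 70.5 h. The time window cannot bring the Day 15 test into the phase.

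**Step 4: count scheduled on-treatment values per subject.** Haematocrit: 3. Every other analyte: 0. With six planned subjects staying to Day 15, that is 0 of 6 with an entry.

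**Step 5: exceptions.** Two routes could produce an isolated entry.
- An unscheduled test before 264 h. SAP 7.8.2 assigns it to the previous scheduled time point, which for these analytes may be the predose one.
- A subject who leaves before 264 h and has the EOT examination at once (Protocol 3.3.4.1). On-treatment then runs to midnight after the termination date and could include that panel.

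Neither fills the table for subjects who follow the schedule.

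**Step 6: the AESI.** The earliest scheduled detection is 336 h (334.5 h with the window). If onset is recorded at or after 264 h, the event is follow-up and is absent from the on-treatment-only displays. If onset is recorded earlier, it stays in them.

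**The case against.** The strongest reply is that nothing is lost. SAP 7.8.2 also promises descriptive statistics over time and for the difference from baseline, with no restriction to the on-treatment phase, and takes the worst value at each planned time point. Day 15 and EOT liver and haemoglobin values therefore enter those summaries. SAP 7 lists all individual values, and Protocol 7.3.3 highlights those outside the reference range. With six subjects (at most eight) and no hypothesis testing, a reader can see every shift in the listings. All of this stands, and it limits the defect to the categorical table.

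The reply on the AESI also largely stands. Assignment is by recorded onset, not by test date. Protocol 5.2.2.1 calls for an unscheduled test when hepatic symptoms occur without results. Appendix 16.1.13.1.8.1 shows follow-up events with a total, and Protocol 7.3.3 requires AESIs and SAEs to be listed separately.

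The phases follow Protocol 7.3.3, which itself sends AEs after the REP to follow-up. But that section also lets the SAP define further intervals, and the SAP adds none.

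Two further readings are tempting but not supported:
- **That the REP is too short because the labelled metabolite M232 is eliminated slowly.** Protocol 1.2.3 defines the REP for BI 425809, by drug levels or pharmacodynamic effects. Protocol 2.3 reports no evidence of pharmacological activity for M232. Protocol 3.2 ties the prolonged sampling to the label carried by M232 and to the release criteria.
- **That the Flow Chart contradicts Protocol 2.3**, which says "this trial requires timely detection, evaluation, and follow-up of laboratory alterations in selected liver laboratory parameters". No interval is attached to that statement, so the schedule does not conflict with it.

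**Conclusion.** The point holds for the shift tables. SAP 7.8.2 specifies an output that SAP Table 6.1: 1 and the Flow Chart together leave without a scheduled post-dose entry for every analyte except haematocrit. Haematocrit, with three on-treatment values per subject, gives partial information on the haemoglobin risk but none on the liver.

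For the AE displays the point is conditional on a recorded onset at or after 264 h. A reader might infer that a hepatic AESI would go unreported, or that no post-dose liver result would be shown. The documents do not support either inference: what is affected is which table shows the result.

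The weight is moderate. Protocol 7.1.1 calls safety an additional main objective, but Protocol 2.2 lists no safety objective and 5.2.1 treats safety parameters as descriptive only.

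The conclusion assumes subjects stay to Day 15 and are tested as scheduled. It also assumes that the internal laboratory display standard (SAP reference 10), which is not available here, does not redefine the last on-treatment value. The SAP states no such exception.

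**What to change.** Change SAP wording only.

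- **SAP 7.8.2:** replace the last on-treatment value in the shift tables with the last, and separately the worst, post-baseline value up to end of trial. State that this includes Day 15, Day 35 if performed, and EOT.
- **SAP 6.1:** in CTR Section 15, show AESIs and SAEs from drug administration to end of trial, beside the existing column for the 11-day period. The other Section 15 AE displays can stay as they are.

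No sample, visit or REP definition changes. The cost is that some late and possibly unrelated values or events enter these displays. For AESIs and SAEs, the 11-day column keeps early and late events distinguishable.
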